6.2 SAFETY ENDPOINTS

Variable	Role	Operational definition
Incidence and severity of treatment-emergent adverse events	Safety outcome	
Discontinuation due to adverse event	Safety outcome	
Discontinuation from Study	Safety outcome	
Serious adverse events	Safety outcome	
Death	Safety outcome	either "intensity according to NCI-CTC-criteria = grade V fatal" or "outcome = exitus" or "event term = death"
Laboratory values (if available)	Safety outcome Subgroup identifier	Hemoglobin, calcium, albumin, LDH, creatinine, ALT, AST, alkaline phosphatase, total bilirubin, TSH, fT3, fT4, hematocrit, phosphate, HbA1c, glucose, neutrophils, lymphocytes, monocytes, eosinophils, basophils, sodium, potassium, magnesium, cholesterol, triglycerides
Global tolerability assessment	Safety outcome	

PFIZER CONFIDENTIAL

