6.4.1 Motzer score

Motzer score

According to the Motzer score five risk factors are defined: low Karnofsky performance status (< 80%), high LDH (> 1.5 times upper limit of normal \equiv > 300 U/L), low hemoglobin (< lower limit of normal \equiv < 13 g/dL for male patients, < 11.5 g/dL for female patients), high corrected serum calcium (> 10 mg/dL) and time from diagnosis to start of Torisel® or Sutent® treatment less than one one year. A patient without any risk factor present at baseline visit belongs to the favorable-risk group, one with one or two risk factors present at baseline belongs to the intermediate-risk group and one with three or more risk factors present at baseline belongs to the poor-risk group.

The corrected serum calcium value will be computed from the values of serum calcium and serum albumin according to the following formula:

Corrected Serum Calcium (mg/dL)

= Calcium (mmol/L) * 4.008 - 0.707 * (Albumin (g/L) / 10 - 3.4).

Modified Motzer score

The modification of the Motzer score adds one further risk factor: at least 2 sites of organ metastases. The assignment to the risk groups and the calculation of corrected serum calcium remains unchanged. Within this study modified Motzer score was only determined for 1^{st} line patients. Only two categories were analyzed " $\geq 3 = \text{poor}$ " and "< 3 = non poor".

Motzer score for previously treated patients

The Motzer score for previously treated patients is based on the three risk factors: low Karnofsky performance status (< 80%), low hemoglobin (< lower limit of normal \equiv < 13 g/dL for male patients, < 11.5 g/dL for female patients) and high corrected serum calcium (> 10 mg/dL). The score is only defined for patients with at least one previous systemic treatment of RCC. A patient is assigned to the favourable-risk groups, if no risk

factor is present, to the intermediate-risk group, if one risk factor is present and to the poor-risk, if two or three risk factors are present.

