7 HANDLING OF MISSING VALUES

Generally, missing values still missing after performing quality improvement measures (edit checks, queries) were performed, will not be replaced

For determining the risk groups according to Motzer score, modified Motzer score and Motzer score for pretreated patients the following procedures will be kept to:

- If at least three (two for Motzer score for pretreated patients) risk factors are present, missing values for the remaining can be ignored and the patient will be assigned to the poor risk group.
- If the calcium value is given, but the albumin value is missing, than calcium will be interpreted as a risk factor if the calcium value is above 11 mg/dL.
- If the hemoglobin value is missing, but a clinically significant low hemoglobin value or anemia is documented as comorbidity, than this will be interpreted as a risk factor present.
- If the LDH value is missing, but a clinically significant high LDH value is documented as comorbidity, than this will be interpreted as a risk factor present.

With the protocol amendment including mRCC patients being treated with axitinib some additional information was asked for in the CRF. This implies missing values for patients documented under earlier versions of protocol and CRF. The percentage of missings due to this reason will not be reported in tables extra. With amendment VI interim treatment with non-Pfizer products was included. This data will only be analyzed for patients documented under amendment VI.

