8 STATISTICAL METHODOLOGY AND STATISTICAL ANALYSES

8.1 STATISTICAL METHODS

8.1.1 Analysis Of Categorical And Continuous Data

Categorical data will be analyzed by presenting frequency tables (absolute and relative frequencies/ adjusted and not adjusted). For continuous data the sample statistics mean, standard deviation, median, minimum and maximum, and quartiles are calculated. For incidence rates 95% confidence intervals will be presented.

Data measured several times during the study are analyzed by visit presenting absolute and relative differences to baseline for numerical data and shift tables for categorical data.

Agreement between the risks assigned to patients by the risk scores and physician's prognosis of patients risk will be measured using Cohens kappa-statistic.

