EQ-5D-TTO will be calculated from EQ-5D raw values according to the following formula (Greiner, W. et al. 2005):

EQ-5D-TTO = 0.999

- 0.099 * (1*Subject has some problems with walking around + 2 * Subject cannot walk around)

- 0.087 * (1*Subject has some problems with self-care + 2 * Subject has extreme problems with self-care)

- 0.112 * (1*Subject states moderate pain or discomfort + 2 * Subject has extreme pain or discomfort)

- 0.129 * (Subject cannot walk around)

- 0.091 * (Subject has extreme pain or discomfort)

- 0.065 * (Subject is extremely anxious or depressive)

- 0.323 * (Subject states major problems in at least one dimension).

EQ-5D-TTO-values range from -0.205 to 0.999.

Laboratory values

Additional queries were written in the following cases:

- calcium > 10 mmol/L
- albumin > 100 g/L
- hemoglobin > 20 g/dL
- LDH < 80 U/L or > 1000 U/L
- albumin in % of total protein.

Laboratory values were set to "missing" if the documented values were outside the ranges given in the following table:

Laboratory parameter	Lower plausibility range	Upper plausibility range
Neutrophils	6%	100%
Lymphocytes	2.5%	85%
Monocytes	-	26%
Eosinophils	-	16%
Basophils	-	5%
Leukocytes	-	28 G/L
Platelets	-	1000 G/L
Hemoglobin*	-	20 g/dL
Creatinine	-	12 mg/dL
Calcium*	-	10 mmol/L
Sodium	-	320 mmol/L
Potassium	-	15 mmol/L
Phosphate	-	4 mmol/L
Magnesium	-	7 mmol/L
ALT (GPT)	1 U/L	1400 U/L

Laboratory parameter	Lower plausibility range	Upper plausibility range
AST (GOT)	1 U/L	1400 U/L
Gamma-GT	1 U/L	1400 U/L
Alkaline Phosphatase	1 U/L	5100 U/L
Total bilirubin	-	25 mg/dL
Albumin	-	100 g/L
LDH*	80 U/L	1000 U/L
Cholesterol	-	26 mmol/L
Triglycerides	-	35 mmol/L
HbA1c	1%	10%
Glucose	-	_**
TSH	-	21 mU/L
beta-2 Microglobulin	-	-

^{*:} Risk factors according to Motzer score will be set prior to check on plausibility.

CYP3A4-inducing and inhibiting substances

A combination of Torisel® and CYP3A4 influencing substances should be handled carefully. Thus documented concomitant medication will be checked manually for CYP3A4 inducing and inhibiting substances by the medical expert.

If the number of patients who received either CYP3A4 inducing or inhibiting substances is sufficiently large, parts of the safety analysis will be repeated for those subgroups.

Comorbidities

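### Laboratory values outside fixed limits are set to missing with no stated exception for query-confirmed values, which truncates the LDH safety summaries, and the removals are not counted

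*SAP*

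**What the plan says.** The laboratory part of SAP Appendix 1 (A1.3) works in two steps. First, "Additional queries were written in the following cases": calcium above 10 mmol/L, albumin above 100 g/L, hemoglobin above 20 g/dL, albumin given as a percentage of total protein, and "LDH < 80 U/L or > 1000 U/L". Second, values are set to missing "if the documented values were outside the ranges given in the following table". The table's limits for calcium, albumin, hemoglobin and LDH are the same numbers as the query triggers. A footnote on hemoglobin, calcium and LDH adds: "Risk factors according to Motzer score will be set prior to check on plausibility".

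LDH is listed among the laboratory safety endpoints in SAP 6.2, and so are the parameters in "TSH, fT3, fT4, hematocrit, phosphate, HbA1c, glucose, neutrophils, lymphocytes". Tables 3.3-1 and 3.3-2 present sample statistics by visit with absolute and relative change from baseline. SAP 8.1.1 defines those statistics: "mean, standard deviation, median, minimum and maximum, and quartiles are calculated". Under SAP 7, values still missing after "quality improvement measures (edit checks, queries) were performed, will not be replaced", and the summary in SAP 8.2.3 excludes missing laboratory data.

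**The concern.** A plausibility filter should remove errors and leave true extremes. This one acts on the size of the value alone. The deletion sentence makes no distinction between a value that the site corrected, one that it confirmed and one that it never answered. Because trigger and limit coincide, every value confirmed on query is still outside the range when the second step is applied.

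For most of the table this may be harmless; the calcium, albumin and hemoglobin limits are not challenged here. LDH is different, because its upper limit is a modest multiple of the cut that the SAP itself uses for high LDH. At stake is the upper end of a safety parameter, which a reader of a safety table looks at first: the largest LDH that Table 3.3-2 can show is 1000 U/L, whatever was measured. The reader cannot see that this has happened, because the visible laboratory shells contain no count of values set to missing, no listing of outliers and no shift table.

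**Working it through.** **1. Query trigger against deletion limit (both in SAP A1.3).**

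| Parameter | Query trigger | Set to missing |
|---|---|---|
| Calcium | > 10 mmol/L | > 10 mmol/L |
| Albumin | > 100 g/L | > 100 g/L |
| Hemoglobin | > 20 g/dL | > 20 g/dL |
| LDH | < 80 or > 1000 U/L | < 80 or > 1000 U/L |

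The plausibility table lists 27 parameters. Glucose and beta-2 microglobulin have no limit, which leaves 25. Four of these are on the additional-query list and 21 are not, among them TSH (limit 21 mU/L), HbA1c (1% to 10%) and neutrophils (6% to 100%).

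**2. Where the LDH limit lies.** SAP 6.4.1 defines one Motzer factor as "high LDH (> 1.5 times upper limit of normal", equated there with more than 300 U/L. The implied upper limit of normal is 300 / 1.5 = 200 U/L. The deletion limit is 1000 / 200 = 5 times that, and 1000 / 300 = 3.3 times the SAP's own cut for high LDH.

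**3. The rule applied to single LDH values.**

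| LDH (U/L) | Queried | Motzer factor | In Table 3.3-2 |
|---|---|---|---|
| 60 | yes | no | no, even if confirmed |
| 400 | no | yes | yes |
| 1000 | no | yes | yes |
| 1001 or 1500 | yes | yes | no, even if confirmed |

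**4. Effect of one deletion on a visit mean.** Let n be the number of values at the visit including the deleted one, x the genuine deleted value and m the average of the others. The true mean is ((n − 1)m + x)/n and the reported mean is m, so the reported mean is too low by (x − m)/n. The documents give neither m nor n. With m = 200 to 300 U/L and n = 50 to 200 as assumptions:

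- x > 1000, m = 300, n = 200: more than 700/200 = 3.5 U/L.
- x > 1000, m = 200, n = 50: more than 800/50 = 16 U/L.
- x < 80 acts in the other direction, by between (m − 80)/n and m/n: from (200 − 80)/200 = 0.6 to 300/50 = 6 U/L.

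**5. Effect on a whole distribution (illustration only).** LDH is assumed lognormal with median 250 U/L. The share above 1000 U/L is set to 1%, 3% or 5%, and values below 80 U/L are deleted as well.

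| Share > 1000 | Mean, all → kept | SD, all → kept | Upper quartile, all → kept |
|---|---|---|---|
| 1% | 299 → 296 | 195 → 167 | 373 → 373 |
| 3% | 328 → 311 | 279 → 192 | 411 → 404 |
| 5% | 357 → 320 | 363 → 205 | 441 → 423 |

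The SD suffers most, the mean less and the upper quartile least.

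**6. Change from baseline.** A deleted follow-up value loses that patient's change at that visit. A deleted baseline value loses it at every visit.

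**The case against.** The strongest reply concerns materiality. Nothing in the documents shows that a genuine LDH above 1000 U/L, TSH above 21 mU/L, HbA1c above 10% or neutrophil share below 6% occurs in this registry; that is a clinical assumption. If the out-of-range values are unit or entry errors, the rule improves the tables. The evaluation is purely descriptive (protocol, Biometric evaluation), there are no hypotheses or decision rules (SAP 4), and an abnormal finding that meets the protocol's criteria still reaches the adverse event tables. All of this stands and limits the size of the point. It does not put a confirmed value back into the laboratory tables.

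The SAP also never says in words what happens to a confirmed value, and the protocol refers to a data validation plan that was not supplied. That confirmed values are lost is therefore read from an unconditional sentence and matching limits. The validation plan may hold further queries, but more queries do not help while deletion does not depend on the answer.

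Two stronger readings are tempting and not supported. A reader might infer that the SAP contradicts itself by counting an LDH of 1500 U/L for the Motzer score and then deleting it. It does not: the score needs only a yes or no at 300 U/L, whereas a mean or maximum is sensitive to one mistyped number, so setting the flag first is coherent. A reader might also infer that patients drop out of the current MIPI groups or the LDH survival strata (300 U/L or less against more). The SAP does not say whether these use values from before or after the check, but no loss is shown, and current MIPI falls back on the physician's documented value when inputs are missing. That order needs a clarification only.

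**Conclusion.** The point holds as a defect in a data-handling rule, of minor to moderate weight. Followed as written, the rule removes every LDH above 1000 or below 80 U/L from Table 3.3-2 whether or not the site confirmed it, and the planned laboratory tables do not show how many values went. For LDH the maximum, minimum, mean, SD and some changes from baseline are affected; medians and quartiles are little affected.

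That the reported range is bounded follows from the SAP text alone. The total effect cannot be estimated, because the documents give no count of affected values. The shift of at least 3.5 to 16 U/L per deleted high value, and the distribution figures, rest on assumed inputs and apply to genuine values only; deleting an error causes no such bias. A reader might infer that the laboratory results as a whole are unreliable. The documents do not support that.

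**What to change.** Amend the deletion sentence in SAP A1.3 so that an out-of-range value on the query list is set to missing only if the query shows an error or stays unresolved, and a value confirmed on query is kept. Report the number of values set to missing per parameter, including those not on the additional-query list such as TSH, HbA1c and neutrophils; for these the present rule can stay as long as the removals are visible. In the same edit, state whether current MIPI and the LDH strata are derived before or after the check.

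The cost is small: one changed sentence, one clarifying phrase and one count table, which SAP 9 would by default repeat for each combination of treatment and indication. The LDH queries already exist, so no new site contact is needed. Duplicate laboratory summaries with and without the out-of-range values are not needed; they would cost more and readmit unqueried errors. There are two downsides. Some entry errors that a site wrongly confirmed may remain, and the final laboratory tables may differ slightly from earlier interim ones, although SAP 3 plans identical content; a footnote can explain this.

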6.4.2 Mantle Cell Lymphoma International Prognostic Index (MIPI)

MIPI score is defined as

Score = $0.0353 * age (yrs) + 0.6978 * [ECOG > 1 {yes/no}] + 1.367*log₁₀(LDH/ULN LDH) + 0.9393*log10(Leukocyte count [/µl])$

Low risk if Score < 5.7

Intermediate risk if $5.7 \le \text{Score} < 6.2$

High risk if $6.2 \le Score$

If all data necessary to compute MIPI score are available, the calculated risk will be used for analyses of current MIPI. Otherwise and for the time of primary diagnosis the value documented by the physician will be used.

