2.2-2	Kaplan-Meier estimates for Overall survival by patient risk groups	MCL	EAS	.1 Risk groups according to MIPI score at time of primary diagnosis .2 Risk groups according to current MIPI score .3 2 nd and 3 rd line .4 2 nd to 4 th line .5 4 th line and beyond .6 5 th line and beyond .7 Patients with OR (CR+PR) .8 Patients with (MR + SD) .9 Patients with clinical benefit (CR+PR+MR+SD) .10 Patients ≤ 65 vs. patients > 65 yrs. including Kaplan-Meier curves .1 OS all patients excluding "not assessable" patients .2 OS patients with OR (CR+PR) vs. (MR+SD) vs. PD .3 OS patients with clinical benefit (CR+PR+MR+SD) vs. PD .4 OS Temsirolimus 2 nd to 4 th line (1 − 3 prior therapies) vs. 5 th line and beyond (≥ 4 prior therapies) .5 OS 2 nd to 3 rd line Temsirolimus (1 − 2 prior therapies) vs. 4 th line and beyond (≥ 3 prior therapies)
2.2-2	Kaplan-Meier estimates for Overall survival by patient risk groups	GIST	EAS	.1 Risk groups according to Fletchers risk table .2 Risk groups according to physician's prognosis
2.2-3	Frequency table of patients status by time window (survival phase)	All	EAS	
2.3	Progression free survival			
2.3-1	Kaplan-Meier estimates for Progression free survival	All	EAS Sequence analysis	Time to 25%, median and 75% survival with confidence intervals including Kaplan-Meier curve on all patients

Table No.	Title	Treatment/ Indication	Analysis set	Description
2.3-2	Kaplan-Meier estimates for Progression free survival by patient risk groups	mRCC	EAS	.1 Physicians prognosis of patients risk .2 Risk groups according to Motzer score .3 Risk groups according to modified Motzer score .4 Risk groups according to Motzer score for pretreated patients .5 by treatment sequence .6 1st line patients .7 1st line patients by risk (poor vs. non-poor) .8 2nd line vs. higher lines .9 2nd vs. 3rd line vs. higher lines .10 patients ≤ 65 yrs vs. > 65 yrs .11 by LDH low (≤ 300 U/l) vs high (> 300 U/l) .12 by histology (clear cell vs. other) Kaplan-Meier curves incl Log-Rank-Test .1 PFS 1st line vs. 2nd line and higher .2 PFS 1st line vs. 2nd line vs. 3rd line and higher .3 PFS ≤ 65 yrs vs. > 65 yrs .4 PFS LDH low (≤ 300 U/l) vs high (> 300 U/l) .5 PFS clear cell histology vs. other histology

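### The SAP's plausibility deletion exempts the Motzer risk factors but not MIPI; read literally, MCL patients with extreme leukocyte or LDH values lose their calculated current MIPI class

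*SAP*

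**What the plan says.** **Deletion rule.** SAP Appendix 1, A1.3 (laboratory values): "Laboratory values were set to 'missing' if the documented values were outside the ranges given in the following table". The table gives leukocytes an upper limit of 28 G/L and no lower limit. LDH has limits of 80 and 1000 U/L.

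**Exemption.** An asterisk on hemoglobin, calcium and LDH leads to the footnote "Risk factors according to Motzer score will be set prior to check on plausibility". Leukocytes carry no asterisk, and MIPI is not mentioned.

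**Queries.** The same section lists additional queries. LDH is on that list, with the same limits as the deletion ("LDH < 80 U/L or > 1000 U/L"); leukocytes are not.

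**MIPI.** SAP 6.4.2 builds the score from age, ECOG, LDH relative to its ULN, and leukocytes. It then says "If all data necessary to compute MIPI score are available, the calculated risk will be used for analyses of current MIPI". Otherwise the physician's recorded value is used. SAP 7 says that remaining missing values are generally not replaced. It gives special rules for incomplete Motzer inputs but none for MIPI.

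**Use.** SAP 5.4 repeats the MCL effectiveness analyses by MIPI group, and SAP 8.1.2 adds log-rank tests. "Risk groups according to current MIPI score" is a stratification in the MCL versions of tables 2.2-2 (overall survival) and 2.3-2 (progression-free survival). Table 2.4 (physician's assessment) is also split by current MIPI.

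**The concern.** The footnote shows that the authors saw the hazard for one score: an extreme but true value should not disappear before it has counted towards the risk group. MIPI has the same exposure, because two of its four inputs have deletion limits, but it gets no such protection. As written, an LDH of 1100 U/L counts as a Motzer risk factor in a renal cell carcinoma patient and is deleted in an MCL patient.

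Whether the calculated class survives therefore depends on the inputs that determine it. If the losses fall mainly at one end of the score, that stratum becomes a mixture of calculated and physician-assigned classes, or loses patients who have no physician value. No table visible in SAP section 9 (some rows are blacked out) counts the classes by source, so a reader could not see how much of this had happened.

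**Working it through.** The documents give no count or figure on this point, so there is nothing to reproduce. The check puts the deletion limits into the SAP's own formula.

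**Inputs**
- Score = 0.0353 × age + 0.6978 × [ECOG > 1] + 1.367 × log10(LDH/ULN) + 0.9393 × log10(leukocytes per µl). Low is below 5.7, high is 6.2 or more (SAP 6.4.2).
- Limits: leukocytes 28 G/L = 28,000/µl; LDH 80 and 1000 U/L (SAP A1.3).
- LDH ULN: not given for MCL. The Motzer definition in SAP 6.4.1 equates 1.5 × ULN with 300 U/L, which implies 200 U/L. Applying this to MCL is an assumption; 250 U/L is tried as well.
- Age: Protocol 5.2 puts most new MCL cases at 60-65 years, and the registry enrols relapsed or refractory disease.

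**Age at which the score becomes high**, with ECOG 0-1:

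age = (6.2 − 1.367 × log10(LDH/ULN) − 0.9393 × log10(leukocytes)) / 0.0353

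*Leukocytes at the limit.* The leukocyte term is 0.9393 × log10(28,000) = 4.177.
- LDH = ULN: (6.2 − 4.177)/0.0353 = 57.3 years
- LDH = 0.8 ULN: (6.2 + 0.132 − 4.177)/0.0353 = 61.1 years
- LDH = 0.7 ULN: (6.2 + 0.212 − 4.177)/0.0353 = 63.3 years

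*LDH at the upper limit*, leukocytes 6,000/µl (term 3.549).
- ULN 200: (6.2 − 0.955 − 3.549)/0.0353 = 48.0 years
- ULN 250: (6.2 − 0.823 − 3.549)/0.0353 = 51.8 years

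**Scores at typical ages** (ECOG 0-1, ULN 200)

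| Age | Leukocytes 28,000/µl, LDH = ULN | Leukocytes 6,000/µl, LDH 1000 U/L | Leukocytes 6,000/µl, LDH = ULN | Leukocytes 6,000/µl, LDH 80 U/L |
|---|---|---|---|---|
| 60 | 6.30 high | 6.62 high | 5.67 low | 5.12 low |
| 65 | 6.47 high | 6.80 high | 5.84 intermediate | 5.30 low |
| 70 | 6.65 high | 6.98 high | 6.02 intermediate | 5.48 low |

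The two upper limits thus remove mainly high scores, and the lower LDH limit removes mainly low ones.

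**How often is an affected patient high risk?** An illustrative simulation used the SAP formula with assumed distributions: mean age 60-70 (SD 9), ECOG > 1 in 15%, median LDH 0.8-1.2 ULN in the leukocyte group, and median leukocytes 6.5 G/L in the LDH group. High risk applied to 95-99% of patients with LDH above 1000 U/L and to 73-97% of those with leukocytes above 28 G/L. These shares rest on the assumptions, not on trial data.

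**The case against.** - **The order of steps is inferred.** No sentence says when MIPI is derived relative to the deletion. A reader might take it as stated that MIPI comes second. The documents support only that a general rule with one named exemption leads there on a literal reading. This stands, and it limits the claim.
- **Leukocytes may still be checked.** A reader might infer that true high counts are deleted unchecked. The SAP list covers additional queries only. Protocol section 8 (Quality Control) provides plausibility checks in a data validation plan, with queries to sites, and that plan is not available here. The inference is not supported.
- **The physician fallback keeps patients in the strata.** If these patients score clearly high, a recorded physician class may well agree, and membership would hardly change. It changes only where the physician value is missing or differs. This stands: it removes any claim of a demonstrated bias, but not the mixing of sources.
- **Not every affected patient is high risk.** At age 60, 28,000/µl and 0.7 ULN, the score is 6.08, which is intermediate. For leukocytes, mostly high risk is the most that can be said.
- **Motzer and MIPI differ in kind.** Motzer factors are yes/no flags, so the size of an extreme value does not matter. MIPI is log-linear: a thousandfold unit error in leukocytes adds 0.9393 × 3 = 2.82 points, against an intermediate band of 6.2 − 5.7 = 0.5. Using unqueried values would let such errors through. This stands and shapes the fix.
- **Limited reach.** The evaluation is descriptive (Protocol section 11), without hypotheses or decision rules (SAP 4). Overall MCL results and the tables by MIPI at primary diagnosis are unaffected.

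**Conclusion.** The point holds in a limited form. Followed literally, the SAP withdraws the calculated current MIPI class from MCL patients with leukocytes above 28 G/L or LDH outside 80-1000 U/L. They receive the physician's class, or none if none was recorded. The withdrawal depends on the score: the upper limits take mostly high-risk patients at the ages expected in MCL, and the lower LDH limit takes mainly low-risk ones. The current-MIPI strata for overall survival, progression-free survival and physician assessment then combine two sources, unevenly across risk groups.

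A reader might go further and conclude that the high-risk curve and the log-rank comparison are shifted. The documents do not support that. They give neither the number of affected patients, which could be zero, nor the agreement between physician and calculated classes, so the size and direction of any shift are unknown.

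The conclusion rests on the inferred order of steps and, for the LDH figures, on an assumed ULN of 200-250 U/L. If the programming already derives MIPI first, the SAP still needs to say so.

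**What to change.** 1. State in SAP A1.3 and 6.4.2 that current MIPI is calculated before the plausibility deletion, using out-of-range leukocyte and LDH values that a query has confirmed.
2. Add leukocytes above 28 G/L to the additional-query list.
3. Where the value is unconfirmed or shown to be an error, use the physician-documented class. This keeps unit errors out of the score.
4. Report how many current-MIPI classes are calculated, physician-documented and missing.

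The cost is a few lines of SAP text, a re-ordered derivation step, one set of counts and a few extra queries.

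### The 10 mmol/L calcium limit cannot catch mg/dL entries, so non-risk values can count as Motzer risk factors; flagging before the check also mis-scores unresolved hemoglobin unit errors

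*SAP*

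**What the plan says.** SAP Appendix 1, A1.3 (Laboratory values) sets a query for "calcium > 10 mmol/L". Its plausibility table gives calcium no lower limit and the same upper limit: "Calcium* - 10 mmol/L". The action on out-of-range results is: "Laboratory values were set to 'missing' if the documented values were outside the ranges given in the following table". Hemoglobin has an upper limit of 20 g/dL for both query and deletion. The asterisk on hemoglobin, calcium and LDH leads to the footnote "Risk factors according to Motzer score will be set prior to check on plausibility".

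SAP 6.4.1 defines the calcium factor as "high corrected serum calcium (> 10 mg/dL)", computed as "Calcium (mmol/L) * 4.008 - 0.707 * (Albumin (g/L) / 10 - 3.4)". Hemoglobin is a factor below 13 g/dL in men and 11.5 g/dL in women. On grouping, "one with three or more risk factors present at baseline belongs to the poor-risk group". In the score for pretreated patients, two of three factors suffice for poor risk.

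SAP Section 7 adds that if albumin is missing, "calcium will be interpreted as a risk factor if the calcium value is above 11 mg/dL". If hemoglobin is missing but anemia or a clinically significant low value is recorded as a comorbidity, the factor counts as present.

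**The concern.** A plausibility limit on a score component should stop values that cannot be right before they enter the score. The calcium limit does not do this for the most foreseeable error, a mg/dL figure recorded as mmol/L. The SAP itself uses both calcium units, and it already has a query for albumin reported as a percentage of total protein, so wrong-unit entries were expected.

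The order of steps raises a second problem. A hemoglobin too high to be believed is first read as evidence against anemia and only then removed.

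Both errors can place mRCC patients in the wrong Motzer group. Those groups carry the log-rank comparisons (SAP 8.1.2), the kappa against physician's prognosis (SAP 8.1.1), the poor-prognosis first-line temsirolimus subgroup (SAP 5.4), and the Motzer-based parts of the survival, response and physician-assessment tables (SAP Section 9).

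**Working it through.** **Inputs.** The conversion and correction formula, the risk cuts and the group rules come from SAP 6.4.1. The missing-data rules come from SAP Section 7. The query and deletion limits and the order of steps come from SAP A1.3. Albumin values are illustrative.

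**1. The cut in mmol/L.** Calcium at the cut = (10 + 0.707 × (albumin/10 − 3.4)) / 4.008. This gives 2.248 at albumin 20 g/L, 2.495 at 34, 2.601 at 40 and 2.777 at 50. At 100 g/L, the highest albumin the SAP accepts, it is 3.659. Any entry above 3.66 mmol/L is therefore flagged whatever the albumin.

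**2. The limit in mg/dL.** 10 × 4.008 = 40.08 mg/dL, and 40.08 / 10 = 4.008 times the cut.

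**3. mg/dL figures recorded as mmol/L, albumin 40 g/L.** The correction is 0.707 × (4.0 − 3.4) = 0.42 mg/dL. For 9.2: 9.2 × 4.008 − 0.42 = 36.45, against a true 9.2 − 0.42 = 8.78.

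| Entry | Corrected value by SAP (mg/dL) | Flagged | Over 10 mmol/L limit | True corrected value (mg/dL) | True risk factor |
|---|---|---|---|---|---|
| 8.0 | 31.64 | yes | no | 7.58 | no |
| 9.2 | 36.45 | yes | no | 8.78 | no |
| 10.0 | 39.66 | yes | no | 9.58 | no |
| 10.01 | 39.70 | yes | yes | 9.59 | no |
| 10.5 | 41.66 | yes | yes | 10.08 | yes |
| 11.0 | 43.66 | yes | yes | 10.58 | yes |

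The first three rows are false flags that no rule in the SAP stops. If albumin is missing they are flagged too: 8 × 4.008 = 32.06, above 11. At low albumin part of the 8-10 range is truly high. At 20 g/L the correction adds 0.99 mg/dL, so the false flags are those up to 9.01.

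**4. Does the order matter for calcium?** For entries up to 10 it makes no difference, because they pass the check anyway. For entries above 10 that are really mg/dL, the flag is correct at albumin 34 g/L or lower. At 40 g/L it is false only from 10.0 to 10.42. With albumin missing it is false only from 10 to 11.

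**5. Hemoglobin.** Take 105 g/L (10.5 g/dL) recorded in g/dL. The true value is below both sex-specific cuts, so the factor is present. As entered, 105 is above 13 and is scored not low. It also exceeds 20, so it is queried and, if the query stays unresolved, set to missing. Section 7 would then look for documented anemia, but the flag was fixed while the value was still there.

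**6. Effect of one false calcium flag on the group.**
- Motzer score: favorable to intermediate with 0 other factors; no change with 1; intermediate to poor with 2.
- Modified score (poor or non-poor): changes only with exactly 2 other factors.
- Pretreated score: favorable to intermediate with 0 others; intermediate to poor with 1.

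A missed hemoglobin factor moves patients the opposite way across the same boundaries.

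**The case against.** A reader might infer from the footnote that flagging first turns rejected calcium values into false risk factors. The documents do not support that as a general claim. As step 4 shows, an entry above 10 that is really in mg/dL is usually a true risk factor. Such entries are also queried, so a wrong flag needs an unresolved query. Deleting all of them before flagging would mainly remove true factors. A decimal slip (25 for 2.5) is another possible cause of a value above 10, so not every such value need be a unit error.

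A second objection is that checks may exist elsewhere. The SAP calls its laboratory queries additional ones. The protocol (Section 8, Quality Control) places plausibility checks in a data validation plan, and the CRF, with its unit fields, is also not available. This stands: one can say only that the SAP states no rule for calcium between the cut and 10 mmol/L.

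It is also tempting to put a percentage on the false flags. With prevalence p of truly high calcium and a share u of entries in mg/dL, the false share is (1 − p)u / (p + (1 − p)u). Assuming p of 8-12% and u of 1, 2 or 5%, this gives 7-10, 13-19 or 27-37%. Those inputs have no basis in the documents, and the formula assumes that no query catches anything. The figures illustrate sensitivity and are not an estimate.

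Finally, not every risk-group table is touched. MCL uses MIPI and GIST uses the Fletcher table. The mRCC tables by physician's prognosis, LDH, line, age, histology or sequence do not use calcium. The evaluation is descriptive, with no hypotheses or decision rules. These limits reduce the reach of the point, but a stated rule can still produce wrong risk groups.

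**Conclusion.** The point holds in two parts. First, a calcium limit of 10 mmol/L is four times the Motzer cut and cannot separate the two units. A non-risk calcium of about 8-10 mg/dL recorded as mmol/L is counted as a risk factor, and nothing in the SAP queries or deletes it. Second, the flag-first order scores an unresolved hemoglobin above 20 g/dL as not low and so bypasses the anemia rule in Section 7.

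The effect is confined to mRCC analyses by Motzer, modified Motzer and pretreated Motzer group. Calcium alone never makes a patient poor-risk. The number of patients affected cannot be computed from the documents. The conclusion assumes that mg/dL entries occur, that they often lie around 8-10, and that no check outside the SAP removes them. It should be corrected, because wrong groups are possible under the stated rules and the remedy is small.

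**What to change.** - Lower the calcium query limit to a value that separates the units and apply it before flagging. For example, 5 mmol/L is 5 × 4.008 = 20.04 mg/dL, twice the cut. Limits of 3.5 or 4 mmol/L (14.03 or 16.03 mg/dL) would also catch entries of 8 to 10.5. The exact value is a judgment for the sponsor.
- Convert entries confirmed as mg/dL and flag on the converted value. Treat only unresolved values as missing.
- Apply the hemoglobin check before flagging. Convert confirmed g/L entries and otherwise treat the value as missing, so that the anemia rule in Section 7 applies.
- Keep the flag-first exemption for LDH, where a value above 1000 U/L may be real and lies well above the 300 U/L cut.
- State whether the data validation plan already holds a calcium unit check. A count of baseline calcium entries between 5 and 10 mmol/L would show the size of the problem directly.

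The cost is a revised footnote, one changed limit and a re-run of the score derivation. The downside is a few extra queries and some risk factors becoming missing.
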